11.4.8.1.4 Post-treatment AEs and SAEs

Post-treatment (S)AEs occurring after the last treatment administration + 15 days up to EOS will be summarized based on the EXTS in a similar manner as described in Section 11.4.8.1.1.

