5 TREATMENTS

5.1 Study treatment

The study treatment is the investigational drug ponesimod. The treatment period consists of an uptitration period (from Day 1 to 14) and a maintenance period (Day 15 until EOT). Ponesimod dose is increased over 15 days until a maintenance dose of 20 mg is reached.

Note that the term "study treatment" or "study drug" refers to study medication provided by the sponsor, as opposed to "commercially available ponesimod" that may be started after discontinuation of study treatment.

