Commercially available ponesimod may be initiated on the day following last intake of study treatment. The start date of commercially available ponesimod must be recorded on the Concomitant Medication page of the eCRF.

In the event that a subject takes any of these forbidden medications, the investigator must contact the sponsor to discuss further FU actions, including stopping/interrupting study treatment as appropriate.

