Other endpoints		
 Absolute values and change from baseline for HR, SBP, DBP and body weight at all assessments 	Y	Y
• Treatment-emergent notable blood pressure abnormalities##	Y	Y
 Absolute values and change from baseline for laboratory tests (hematology, blood chemistry, urinalysis) at all assessments 	Y	Y
• Treatment-emergent notable laboratory abnormalities##	Y	Y
 Change from baseline to EOS versus change from baseline to EOT in lymphocyte counts (absolute and percent change)** 	Y	N
• Treatment-emergent eC-SSRS suicidal ideation score of 4 or above, or a "yes" response on the eC-SSRS suicidal behavior item	Y	N

Cumulative safety data, i.e., AEs for the combined analysis period will only be presented for subjects who received 20 mg ponesimod in the core study.

The selection of AEs of special interest [see Appendix 4] is based on the anticipated risks of treatment with ponesimod; the final list of AEs of special interest will be defined in the SAP.

The selection of notable abnormalities considered for the analyses is based on standard definitions and the anticipated risks of treatment with ponesimod; the final list of abnormalities will be defined in the SAP.

^{**} Only for subjects who have no exposure to commercially available ponesimod prior to the EOS visit.

AE = adverse event; DBP = diastolic blood pressure; DL_{CO} = diffusing capacity for the lungs measured using carbon monoxide; eC-SSRS = electronic self-rated version of the Columbia-Suicide Severity Rating Scale; ECG = electrocardiogram; EOS = End-of-Study; EOT = End-of-Treatment; FEV_1 = forced expiratory volume in 1 second; FVC = forced vital capacity; HR = heart rate; QTcB = QT corrected for heart rate on the basis of Bazett's formula; QTcF = QT corrected for heart rate on the basis of Fridericia's formula; SAE = serious adverse event; SAP = statistical analysis plan; SBP = systolic blood pressure.

15 March 2022, page 89/216

Confidential

EudraCT 2016-004719-10 EDMS-ERI-207656619

The treatment-emergent period is defined as the time from first ponesimod administration in the applicable Analysis Period up to 15 days (inclusive) after last study treatment administration. This definition applies regardless of whether the subject receives commercially available ponesimod after completing study treatment.

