8.4.1 EOS Visit

This visit will be conducted 30–44 days after the permanent discontinuation of study treatment. All assessments should be conducted within the visit window. The last assessment conducted for the study will define the visit date.

The EOS visit should also be conducted for subjects who have switched to commercially available ponesimod.

The visits include:

- EDSS/FS
- MS relapse
- Recording of changes in concomitant medications
- Assessment and recording in the eCRF of methods of contraception (for WOCBP only)
- Body temperature
- SBP/DBP
- 12-lead ECG
- Ophthalmological examination (under the responsibility of the ophthalmologist)
- OCT (under the responsibility of the ophthalmologist)⁶
- Spirometry
- DL_{CO} (if applicable; under the responsibility of the pulmonologist)
- Hematology, blood chemistry, and (following approval of protocol version 5) a serum sample for immunogenicity evaluations (e.g., anti SARS-CoV-2 antibody testing) will be collected for all subjects
- Urinalysis
- Serum pregnancy test for WOCBP
- Recording of AEs and SAEs
- Remind WOCBP and fertile men to use the methods of contraception defined for this study until 6 weeks after the first of two consecutive tests confirming plasma teriflunomide level <0.02 mg/L[#] if such test results have not been obtained prior to EOS visit.

Important note: Teriflunomide testing is no longer required with the approval of protocol version 5

Scheduled OCT assessments are only applicable to Global Protocol version 1 to 5. The requirement for OCT assessments was removed from Protocol Version 6 onwards.

EudraCT 2016-004719-10 EDMS-ERI-207656619

Confidential

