10.1.5 Reporting of adverse events

All AEs occurring after study treatment start (Day 1) and up to 30 days after permanent study treatment discontinuation (i.e., EOS) must be recorded on specific AE pages of the eCRF. This also applies to AEs occurring during the treatment interruption (e.g., due to planned pregnancy), for example, all AEs during study treatment interruption should be reported in the eCRF. If, during study treatment interruption which lasted >30 days the subject fulfills the criteria for permanent study treatment discontinuation, the reporting of AEs should continue until the EOS visit, which should be scheduled as soon as possible after the decision for permanent study treatment discontinuation has been taken. The sponsor may contact the investigator to obtain further information concerning AEs.

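### The post-treatment AE table pools subjects who may already be taking commercial ponesimod with subjects who have stopped, so any off-drug signal is diluted by the unstated share who switched

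*Protocol*

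**What the plan says.** All references are to the protocol.

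**The table.** Section 11.4.8.1.4: "Post-treatment (S)AEs occurring after the last treatment administration + 15 days up to EOS will be summarized based on the EXTS". The population is the whole Extension Set, with no restriction or split.

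**What counts as treatment.** Under section 5.1 the term study treatment "refers to study medication provided by the sponsor, as opposed to" commercial ponesimod.

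**Switching.** Under section 3.2.3.1, a subject whose country gets access before week 240 counts as having completed the study and moves to commercial supply if he or she wants to continue. Section 5.2.3: "Commercially available ponesimod may be initiated on the day following last intake of study treatment". The same section makes switchers identifiable: "The start date of commercially available ponesimod must be recorded on the Concomitant Medication page of the eCRF". They remain in follow-up, as section 8.4.1 states: "The EOS visit should also be conducted for subjects who have switched to commercially available ponesimod".

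**The restriction used elsewhere.** A footnote to Table 9 (section 6.2) limits the EOT-versus-EOS endpoints for FEV1/FVC, DLCO and lymphocytes: "Only for subjects who have no exposure to commercially available ponesimod prior to the EOS visit". Sections 11.4.8.3.1, 11.4.8.3.3 and 11.4.8.5 repeat it.

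**Timing.** Section 8.4.1 on EOS: "This visit will be conducted 30–44 days after the permanent discontinuation of study treatment". Section 10.1.5 requires AEs "up to 30 days after permanent study treatment discontinuation (i.e., EOS) must be recorded".

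**The concern.** A reader will take a table of post-treatment events as a description of what happens once ponesimod is stopped. For a subject who moved straight to commercial supply, the whole window is time on the same drug from a different source. Pooling that subject with one who has stopped mixes two opposite exposure states. An excess of events after stopping would look smaller than it is, and events occurring on the drug would be read as belonging to the period off it.

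Switching is a planned route to completion, so the number affected need not be small. The protocol also recognises the problem, since it removes the same subjects from its other comparisons that depend on being off drug.

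The end of the window raises a lesser question. The table runs to the EOS visit, which may fall as late as day 44, while AE recording is stated to 30 days.

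**Working it through.** The protocol gives no figure for this point, so there is none to reproduce. Days are counted from the last dose of study treatment.

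**1. Exposure in the window.** The table opens on day 16. The half-life is about 32 h (section 1.3.2.1). By the end of day 15 a subject who stopped has passed 15 × 24 / 32 = 11.25 half-lives, leaving 0.5^11.25 = 0.0004, about 0.04% of drug. A switcher may have been back on ponesimod since day 1. The two groups therefore differ almost completely in exposure throughout the window.

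**2. Dilution.** Let f be the share of subjects on commercial ponesimod (not stated in the protocol; range assumed) and R the true ratio of off-drug to on-drug event frequency (assumed). The pooled frequency relative to on-drug is

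seen ratio = (1 − f) × R + f,

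so the excess R − 1 shrinks to (1 − f)(R − 1).

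| f | seen if R = 1.5 | seen if R = 2.0 |
|---|---|---|
| 0 | 1.50 | 2.00 |
| 0.25 | 1.375 | 1.75 |
| 0.50 | 1.25 | 1.50 |
| 0.75 | 1.125 | 1.25 |
| 0.90 | 1.05 | 1.10 |

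This assumes that every switcher has started by day 16, that both groups have windows of equal length, and that switchers have the on-drug event frequency.

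**3. End of the window.** Window length = EOS day − 15. Days beyond the 30-day limit = EOS day − 30.

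| EOS on day | window (days) | beyond day 30 | share |
|---|---|---|---|
| 30 | 15 | 0 | 0% |
| 37 | 22 | 7 | 7/22 = 32% |
| 44 | 29 | 14 | 14/29 = 48% |

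The protocol gives no expected distribution of EOS days, so only the range can be stated.

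**The case against.** **The table follows the protocol's definitions.** Study treatment means sponsor-supplied drug. Sections 6.2, 10.1.1 and 11.1.4.1 say openly that the treatment-emergent window ignores commercial ponesimod. This table is the complement of that window and ensures that later events are tabulated. That stands as far as it goes: a reader might infer that the protocol classes switchers as off drug, and it does not. But those sentences govern events up to day 15. They do not say how events after day 15 should be read, and section 11.4.8.1.4 does not repeat them.

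**Withdrawal is not an objective.** The safety objectives concern long-term safety and re-initiation, Table 9 does not list post-treatment AEs, and all analyses are descriptive. This is correct and limits the weight of the point. It does not make a pooled table easier to interpret.

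**The split is SAP detail.** Section 11 leaves displays to the SAP, which is not at hand and may add one. However, the protocol fixes this table's population and window itself, and it writes the commercial-exposure restriction into its own text for the parallel analyses. Its silence here suggests that no restriction applies.

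**The 30-day mismatch is only wording.** This largely stands. Section 10.1.5 and note 13 to Table 1 equate the 30-day limit with EOS, and section 8.4.1 lists AE and SAE recording at the EOS visit. Section 10.1.5 also continues collection to the EOS visit when an interruption of more than 30 days becomes permanent. On the other side, section 10.2.2 and note 7 to Table 2 say 30 days without mentioning EOS, and section 10.2.4 then asks only for related new SAEs. A loss of data is not shown, but the texts do not agree.

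**Conclusion.** As written, section 11.4.8.1.4 mixes time on ponesimod with time off it, and this is inconsistent with how the protocol treats its other off-drug comparisons. The table keeps only a fraction 1 − f of any off-drug excess. Because f is not stated, the size of the dilution cannot be fixed; the ratios shown are illustrations under assumed values.

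A reader might go further and infer that the table cannot show anything about the period after stopping. The documents do not support that. Subjects who discontinue early, or who finish without switching, contribute genuine off-drug time, and the recorded start dates allow them to be separated. Nor does it follow that about half the window lies outside AE collection: 48% is the extreme for EOS on day 44, and the figure is 0% for EOS on day 30.

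No main endpoint or hypothesis is affected. The change is still worth making, because it alters what a safety table can say and uses data that the protocol already requires.

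**What to change.** **Main change.** In section 11.4.8.1.4, present post-treatment (S)AEs split by exposure to commercial ponesimod before the EOS visit, and name the unexposed group as the post-treatment summary. This carries over the condition already used in Table 9. It takes one sentence and one by-group column, with no new data, because the commercial start date is already mandatory in the eCRF. The downside is a smaller unexposed group and so less precise percentages; events in switchers remain visible in their own column.

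**Secondary change.** Align the end of the table with AE collection in one of two ways:

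- End the table at day 30. This gives every subject followed to EOS the same 15-day window, but leaves later events recorded at EOS to the listings.
- State that AEs and SAEs are collected to the EOS visit. This keeps the table as it is, but sections 10.1.5, 10.2.2 and 10.2.4 and the notes to Tables 1 and 2 must then say the same thing.

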11.4.8.1.5 Deaths

Fatal SAEs occurring any time after the start of treatment in the extension study will be summarized by core study treatment and overall, based on the EXTS in a similar manner as described in Section 11.4.8.1.1.

11.4.8.2 Cardiac safety

11.4.8.2.1 Treatment-emergent abnormalities

Treatment-emergent morphological ECG abnormalities will be summarized in a similar manner to AEs, and will include the cardiac safety events:

- Treatment-emergent QTcF >450 ms, >480 ms, >500 ms
- Treatment-emergent QTcF increase from baseline >30 ms, >60 ms
- Other treatment-emergent abnormalities observed by 12-lead ECG
- Treatment-emergent (serious) cardiac AEs of special interest.

11.4.8.2.2 Absolute values and change from baseline by visit

Descriptive summary statistics for observed treatment-emergent absolute values and absolute change from core baseline in numeric 12-lead ECG values for the parameters HR, PR, QRS, QT, QTcB and QTcF by visit will be provided for the Combined Analysis Period by core study treatment using the SAF.

In addition, descriptive summary statistics by core study treatment and overall for absolute change from extension baseline for pre-dose parameters by visit will be provided for the Extension Analysis Period using the EXTS.

11.4.8.2.3 Change from pre-dose to post-dose

The change from pre-dose to post-dose assessments at 1 h, 2 h, 3 h, and 4 h on the day of initiation of ponesimod in the extension study will be summarized by core study treatment and overall for the following parameters: HR, PR, QT, QTcB, QTcF. This analysis will be based on the Extension Analysis Period using the EXTS.

EudraCT 2016-004719-10 EDMS-ERI-207656619

Confidential

11.4.8.3 Pulmonary safety

15 March 2022, page 142/216

11.4.8.3.1 Absolute values and change from baseline

Descriptive summary statistics by visit for the Combined Analysis Period using the SAF will be provided for observed (absolute and percent of predicted) treatment-emergent values and changes from core baseline for FEV₁, FVC and FEV₁/FVC ratio (all expressed in absolute change, % change).

The mean (and 95% CIs) for change from core baseline to EOS and from core baseline to EOT for FEV_1 and FVC (absolute change, percent change and absolute change in % predicted)** will be plotted by core study treatment for the Combined Analysis Period using the SAF.

11.4.8.3.2 Treatment-emergent decreases in FEV₁ and FVC

The number and proportion of treatment-emergent decreases of % of predicted FEV_1 or FVC > 20 percentage points from core baseline at any time during the Combined Analysis Period for subjects who received ponesimod 20 mg in the core study based only on the SAF will be summarized in a similar manner to the AEs as described in Section 11.4.8.1.1.

11.4.8.3.3 Reversibility of treatment-emergent decreases in FEV₁ and FVC

For the subset of subjects with a decrease of ≥200 mL or ≥12% in FEV1 or FVC from core baseline at EOT, the number and percentage of subjects with a decrease of <200 mL and <12% from core baseline to EOS** in FEV1 or FVC will be summarized for subjects who received ponesimod 20 mg in the core study only for the Combined Analysis Period using the SAF.

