3.2.4 Safety follow-up

For an individual subject, End-of-Study (EOS) is reached when treatment and safety FU have been completed. The EOS Visit should be performed 30–44 days after the permanent discontinuation of study treatment. If during study treatment interruption, the subject fulfills the criteria for

[figure not shown]
15 March 2022, page 52/216

premature discontinuation, the EOS visit should be scheduled as soon as possible after the decision to prematurely discontinue has been taken.

The EOS visit and all assessments will also be conducted for subjects who have switched to commercially available ponesimod.

The overall study design is depicted in Figure 1.

Figure 1 Study design

EOT = End-of-Treatment; EOS = End-of-Study; V = Visit; FU = Follow-up; - - - = no study treatment.

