6.2 Safety endpoints

In order to investigate the long-term safety of ponesimod and the changes in safety in teriflunomide subjects switching to ponesimod 20 mg, analysis will be performed on all data in the core and extension studies combined, using the core baseline as a reference. In addition, safety data

15 March 2022, page 87/216

reference.

EudraCT 2016-004719-10 EDMS-ERI-207656619

Confidential

collected in the extension study will be analyzed independently, using the extension baseline as a

Table 9 details which endpoints will be analyzed for the Extension Analysis Period, and which for the Combined Analysis Period.

Table 9 Analysis of safety endpoints

Endpoints	Combined Analysis Period	Extension Analysis Period
Adverse events		
 Treatment-emergent AEs, SAEs, and AEs of special interest[#] AEs leading to premature discontinuation of study treatment 	Y* Y	Y Y
Cardiac safety		
• Treatment-emergent morphological ECG abnormalities (as defined by the ECG provider)	Y*	Y
 Absolute values by visit for 12-lead ECG parameters (HR, PR, QRS, QT, QTcB, QTcF) 	Y	Y
 Change from baseline values by visit for ECG parameters (HR, PR, QRS, QT, QT QTcB, QTcF) 	Y	Y
 Change in ECG parameters (HR, PR, QRS, QT, QT QTcB, QTcF) from pre-dose to selected post-dose assessments (1 h, 2 h, 3 h, 4 h) on Day 1 and on day of re-initiation of study treatment 	N	Y
Pulmonary safety		
• Absolute values and percent change from baseline in FEV ₁ and FVC at all assessments	Y	Y
• Treatment-emergent decrease from baseline $>20\%$ and $>30\%$ in FEV ₁ or FVC	Y	Y
• Treatment-emergent decrease from baseline >20 percentage points in % of predicted FEV ₁ and FVC	Y	Y
• Among subjects with a decrease of ≥ 200 mL or $\geq 12\%$ in FEV ₁ or FVC from baseline to EOT, reversibility defined as a decrease of < 200 mL or $< 12\%$ in FEV ₁ or FVC from baseline to EOS**	Y	N

15 March 2022, page 88/216

EudraCT 2016-004719-10 EDMS-ERI-207656619

Confidential

Table 9

Analysis of safety endpoints

Endpoints	Combined Analysis Period	Extension Analysis Period
 Absolute change from baseline to EOS versus change from baseline to EOT in FEV₁ and FVC (absolute and % of predicted)** 	Y	N
• Change in lung diffusion capacity as assessed by DL _{CO} (at selected sites only) expressed in absolute change (mL) and % of predicted value from baseline at all assessments	Y	Y
• Change from baseline to EOS versus change from baseline to EOT in DL _{CO} (absolute and % of predicted) (at selected sites only)**	Y	N

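### The lung-function reversibility percentage uses one cut-off for entry and exit, requires no minimum recovery and does not count new falls, so it is positive even if stopping the drug changes nothing

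*Protocol*

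**What the plan says.** Section 11.4.8.3.3 defines the denominator: "For the subset of subjects with a decrease of ≥200 mL or ≥12% in FEV1 or FVC from core baseline at EOT". The numerator is "the number and percentage of subjects with a decrease of <200 mL and <12% from core baseline to EOS", again in FEV1 or FVC. The result "will be summarized for subjects who received ponesimod 20 mg in the core study only", over the Combined Analysis Period in the Safety Set. Subjects exposed to commercial ponesimod before EOS are left out.

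Table 9 (Section 6.2) lists the same endpoint with a different connective: "reversibility defined as a decrease of < 200 mL or" under 12%.

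On timing, Section 3.2.4 states: "The EOS Visit should be performed 30–44 days after the permanent discontinuation of study treatment".

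Section 11.4.8.3.1 has a companion analysis, plotted by core treatment: "The mean (and 95% CIs) for change from core baseline to EOS and from core baseline to EOT". It covers absolute change, percent change and change in percent of predicted.

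**The concern.** For a single parameter, the exit condition in Section 11.4.8.3.3 is the exact complement of the entry condition, and both are measured from the same core baseline. A subject 205 mL below baseline at EOT and 195 mL below at EOS counts as reversed after a 10 mL change. No confirmatory test is required.

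Entry depends on one low EOT reading, so entrants' EOT errors tend to be unfavourable and their EOS readings will on average be higher. Movement the other way, from above the line at EOT to below it at EOS, is not tabulated, and no comparator group shows the chance rate. The table would therefore report reversal both if the drug had no lung effect and if its effect were permanent. It sits under a heading that names reversibility, so the percentage will be read as evidence that the effect goes away after stopping.

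**Working it through.** **The plan's own figure.** The protocol states no expected reversal rate, so there is nothing to reproduce.

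**Inputs from the protocol.** Entry is a decrease of at least 200 mL or at least 12%. Exit under Section 11.4.8.3.3 is a decrease under 200 mL and under 12%. EOS is 30–44 days after stopping.

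**Inputs assumed, because the protocol gives none.** Within-subject test SD *s* is 60–150 mL. Mean lasting decline *m* is 0–300 mL. Between-subject SD of that decline *t* is 0–300 mL. Mean baseline is 3.2 L for FEV1 and 4.0 L for FVC, with a correlation of 0.6 between them.

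**Model with no effect of stopping.**
- Decrease at EOT = T + e0 − e1, and decrease at EOS = T + e0 − e2.
- T ~ N(m, t²) is the same at both visits, so it can include ageing and any permanent drug effect. The errors e0, e1 and e2 are independent with SD *s*.
- Each decrease has variance t² + 2s². Their correlation is (t² + s²)/(t² + 2s²).
- The 12% limit is stricter than 200 mL only below a baseline of 200/0.12 = 1,667 mL, so 200 mL is used as the line for one parameter.
- False reversal rate = P(EOS decrease < 200 | EOT decrease ≥ 200), from the bivariate normal.

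**Results, one parameter, rule of Section 11.4.8.3.3.**

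| Scenario | Share counted as reversed |
|---|---|
| No true decline (m = 0, t = 0), s = 60, 80, 100, 120, 150 | 87%, 78%, 71%, 65%, 59% |
| Common decline of 200 mL, any s | 33.3% |
| Common decline of 300 mL, s = 60 to 150 | 9% to 22% |
| m = 0, t = 150, s = 100 | 41% |
| m = 100, t = 150, s = 100 | 31% |
| m = 200, t = 150, s = 100 | 22% |
| m = 100, t = 250, s = 100 | 20% |
| Grid of 150 cells, m 0–300, t 100–300, s 60–150 | 7% to 53%; 19% of cells reach one third |

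**Check that needs no assumed SD.** If stopping changes nothing and the test errors at EOT and EOS have the same distribution, the two readings are exchangeable. Then P(below at EOT, not below at EOS) = P(not below at EOT, below at EOS), whatever *s*, *m* and *t* are. Simulation agrees, as shares of all subjects:
- m = 100, t = 150, s = 100: 9.9% reversed, 9.8% newly fallen.
- m = 200, t = 150, s = 100: 11.1% and 11.1%.
- m = 100, t = 250, s = 100: 7.5% and 7.5%.

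The plan reports the first cell only. The difference between the cells is zero apart from simulation error.

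**Effect of FEV1 or FVC at exit.** Over 24 joint scenarios, 32% to 76% count as reversed if either parameter under the line is enough, and 5% to 36% if both must be under it. On the first reading, a subject who enters on FVC can leave on an FEV1 that never fell.

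**Effect of the Table 9 wording.** With or at exit, a 250 mL fall from 3.2 L meets entry (at least 200 mL) and also meets exit, since 250/3,200 = 7.8%. For FEV1, 36% to 84% of entrants already satisfy the exit rule on their own EOT value, and 41% to 86% are counted as reversed.

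**The case against.** The strongest reply has three parts.

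First, the percentage is not the only reversibility analysis. Section 11.4.8.3.1 plots mean changes to EOT and to EOS with 95% CIs by core treatment, including percent of predicted, which allows for ageing. Those means are not selected on a low EOT value. This stands, and it limits the damage. It does not supply the chance rate of the responder percentage or correct it.

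Second, the study is descriptive with no pre-specified hypotheses, and detailed definitions of safety variables are left to the SAP. No error rate is at stake. But the protocol does not leave this rule open: it states the entry and exit limits, and following them exactly gives the biased figure.

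Third, the size depends on assumptions. This also stands. A reader might infer that noise alone makes at least one third of the subset look reversed. The documents do not support that as a general statement. It holds for one parameter if there is no true decline or a common one up to 200 mL, and it fails in 81% of the grid cells once decline varies between subjects. A reader might also infer that ageing puts the average subject close to the 200 mL line. That needs the longest possible follow-up and a high assumed ageing rate, whereas Section 3.2.3.1 lets treatment end earlier.

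**Conclusion.** The point holds as a fault in a stated rule. Section 11.4.8.3.3 returns a positive reversal percentage when stopping treatment has no effect, because it selects on a low EOT value, uses one line for entry and exit, and counts crossings in one direction only. That conclusion needs only some test error and EOT and EOS readings that are exchangeable when stopping has no effect.

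The size is assumption-dependent: about 7% to 53% of the subset when true decline varies between subjects, and 59% to 87% with no true decline, for test SDs of 60–150 mL.

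It would go too far to say that the plan has no sound evidence on pulmonary reversibility, since the unselected mean changes remain. The narrower conclusion is that this percentage, taken alone, cannot separate recovery from noise. The and/or conflict between Section 11.4.8.3.3 and Table 9 is a separate contradiction that needs no assumption. It should be settled at the same time.

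**What to change.** In Section 11.4.8.3.3 and Table 9, replace the one-way percentage, or accompany it, with the full EOT-by-EOS cross-table (below / not below the cut-off):
- FEV1 and FVC separately, with the same parameter at entry and exit;
- all core-ponesimod subjects with both values and no commercial ponesimod before EOS, not only those below the line at EOT;
- net reversal = (b − c)/n, where b is the number reversed, c the number newly fallen and n the number with both values. Give a paired 95% CI, for example with SE = √(b + c − (b − c)²/n)/n.

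Use one connective in both places. Under and, entry and exit are complementary for one parameter. Under or, the same value can satisfy both.

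A percent-of-predicted version is optional. A minimum-recovery rule alone is a weaker remedy: over the 24 FEV1 scenarios it lowers false reversal from 7–44% to 4–40% (at least 100 mL) or 0.4–28% (at least 200 mL), and does not remove it.

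The cost is a wording change and one extra table from data already collected. The headline reversal figure will be smaller.
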